Given these shortcomings in this evolving area of clinical research, a comprehensive characterization of myocardial injury in patients with COVID-19 infection and the identification of clinical predictors for its occurrence could allow the development of predictive models, thus helping clinicians in the disease phenotyping and the early assessment of the risk of unfavourable outcome and improving a fast determination of most appropriate treatments and clinical paths, efficient planning and use of clinical resources in terms of treatment type and units (such as intensive care or coronary intensive care). In addition, the identification of clinical predictors and/or protective factors for myocardial injury in COVID-19 infection may pave the way for the development of specific therapeutic strategies aiming to reduce the impact of myocardial injury on COVID-19-related morbidity and mortality. Finally, assessing the long-term cardiovascular impact of myocardial injury in COVID-19 infection could help clinicians in the prognostic stratification and the choice of therapeutic strategies in the post-acute COVID-19 phases, possibly identifying those patients that may need a more aggressive therapy and a closer follow-up.

A comprehensive characterization of myocardial injury in COVID-19 infection is still lacking, and no clinical predictors of myocardial injury has been identified yet. Moreover, the long-term cardiovascular outcome of myocardial injury in the post-acute COVID-19 phase is largely unknown. We thus hypothesize that:

- that clinical predictors and/or protective factors (including vaccination status) for myocardial injury in COVID-19 infection could be identified, thus allowing the development of predictive models that could help clinicians in the disease phenotyping,

the early assessment of the risk of unfavourable outcome and improving a fast determination of most appropriate management;

- that myocardial injury in COVID-19 patients could be associated with a worse clinical course characterized by higher incidence of in-hospital complications and need for escalation of therapies;
- that myocardial injury in COVID-19 patients could be associated with a worse angina status and quality of life as well as with a higher rate of adverse cardiovascular events in the post-acute COVID-19 phase, thus helping in the prognostic stratification of COVID-19 patients and identifying those that may need a more aggressive therapy and a closer follow-up.

OBJECTIVES

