Primary objective

To identify clinical predictors of myocardial injury in patients hospitalized for COVID-19 infection since the introduction of vaccines (i.e., March 1, 2021).

Secondary objectives

1. To evaluate if the presence of myocardial injury during the index hospitalization for COVID-19 is associated with a worse in-hospital clinical course in terms of in-hospital complications and need for aggressive therapies.
2. To evaluate if the presence of myocardial injury during the index hospitalization for COVID-19 are associated with a worse angina status and quality of life (evaluated using the Seattle Angina Questionnaire [SAQ] summary score (15)) at 12-months follow-up.
3. To evaluate if the presence of myocardial injury during the index hospitalization for COVID-19 predicts a worse clinical outcome in terms of major adverse cardiovascular events (MACE) (defined as the composite of cardiovascular death, ischemic heart disease [acute or chronic coronary syndromes], stroke/transient ischemic attack [TIA] and hospitalization for heart failure), dysrhythmias (defined as the composite of new-onset atrial fibrillation and/or ventricular arrhythmias), inflammatory heart disease (pericarditis and/or myocarditis) or thrombotic disorders (pulmonary embolism, deep vein or superficial vein thrombosis) at 12-months follow-up.

METHODS

Study design

Retrospective and prospective observational study.

Population

All consecutive patients hospitalized at Policlinico Universitario A. Gemelli IRCSS since March 1, 2021, with a diagnosis of SARS-CoV-2 infection (≥ 1 positive nasopharyngeal swab) and at least one value of high-sensitivity cardiac troponin I (hs-cTnI) measured during the index hospitalization will be enrolled. Given that the patients are unable to physically sign the informed consent form due to epidemiological reasons (contamination of papers by SARS-CoV-2), each patient will verbally declare the consent to “Consenso al trattamento dei dati personali e dei campioni biologici a scopo di ricerca – no profit”, “modulo di dichiarazione della volontà espresso ai fini del consenso informato generale alle cure” and “modulo dossier sanitario – richiesta di oscuramento/deoscuramento di eventi/episodi” at the presence of at least two witnesses.

Inclusion criteria

- Age ≥ 18 years;
- Overt COVID-19 infection (molecular nasopharyngeal swab positive for SARS-CoV-2 ≥ 1);

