1. The occurrence of myocardial injury during the index hospitalization for COVID-19 infection will be correlated with in-hospital complications (defined as the composite of the need for non-invasive or invasive ventilation, access to intensive care unit, length of hospitalization, use of glucocorticoids or antibiotics, and death).
2. The occurrence of myocardial injury in patients during the index hospitalization for COVID-19 infection will be included in a prediction model and correlated with future cardiovascular events (MACE), dysrhythmias, inflammatory heart disease and/or thrombotic disorders at 12-months follow-up.
3. The occurrence of myocardial injury during the index hospitalization for COVID-19 infection will be correlated with angina status and quality of life, evaluated using the SAQ summary score, at 12-months follow-up.

STATISTICAL ANALYSIS PLAN

Sample size calculation

A comprehensive characterization of myocardial injury in COVID-19 infection is still lacking, and no clinical predictors of myocardial injury has been identified yet. Moreover, the long-term cardiovascular outcome of myocardial injury in the post-acute COVID-19 phase is largely unknown. Thus, this configures as a pilot study on large-scale cohort. As such no formal sample size calculation is needed. However, based on the COVID-19 datamart of our clinical institution and on inclusion criteria, we expect to include in the study around 2000 patients hospitalized with COVID-19. Such a sample size is largely consistent with common rules of thumb for pilot studies. In addition, the estimated sample size is largely consistent with the van Smeden metamodels related to the new statistical approaches for the development of clinical prediction models (17). The square root of the mean squared prediction error (rMPSE) and mean absolute prediction error (MAPE) may be approximated via the results of these. Lower values for rMSPE and MAPE indicate better performance. For instance, at a sample size of $N=400$, with $P=8$ candidate predictors and an expected event fraction of $\frac{1}{4}$, the predicted out-of-sample rMPSE would be 0.065 when ML model (without variable selection) is applied, and 0.053 for Ridge regression; MAPE would instead be 0.045 for the ML model and 0.038 for the Ridge regression.

Statistical analysis

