All demographic, clinical and laboratory characteristics will be summarized by descriptive statistics techniques. In depth, qualitative variables will be expressed by absolute and relative percentage frequencies. Quantitative variables, indeed, will be reported either as mean and standard deviation (SD) or median and interquartile range (IQR), respectively in the case they were normally or not normally distributed. Their distribution will be previously assessed by the Shapiro Wilk test. Between groups differences in the demographic, clinical, laboratory and pathologic features will be assessed by the Chi Square or the Fisher's exact test as for qualitative variables, with Yates correction, as appropriate, whilst quantitative variables will be evaluated either by the Student's t test or the Mann-Whitney U test, according to their distribution. Univariable and multivariable logistic regression models will be performed to evaluate the presence of clinical predictors for the occurrence of myocardial injury in COVID-19 infection. Results will be expressed as odds ratio (OR) with 95% confidence interval (CI). Model calibration performances will be evaluated via the Hosmer-Lemeshow goodness of fit test with 10 groups. Model performance will be assessed through receiver-operator characteristic (ROC) curve analysis by reporting the area under the curve, sensitivity, specificity and +/- likelihood ratio (LR). Univariable and multivariable logistic regression analysis will be performed also to assess the association of myocardial injury in COVID-19 infection with in-hospital complications and need for aggressive therapies.

Univariable and multivariable multiple linear regression will be instead used to assess

whether SAQ summary score at 12-months follow-up is affected by myocardial injury in patients with COVID-19 infection.

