Finally, to assess whether the presence of myocardial injury during COVID-19 predicts a worse outcome, in term of both MACEs at 12 months and single components, uni- and multivariable interaction proportional hazard Cox regression models will be computed. We will consider, as for MACEs, time to first event, and for each component, time to each event. To evaluate combined effects between each clinical/laboratory predictor and presence/absence of Myocardial Injury (MI), multivariable interaction Cox models will be fitted, and the interaction hazard ratios (IHR) evaluated. In particular, for each predictor, one interaction Cox model will be fitted. In this framework, IHR = 1 indicates no synergy between predictor and MI, IHR <1 expresses a reduction of hazard due to the synergy, while IHR >1 an increased hazard. The interaction parameters (IHR) will be interpreted as difference (in HR terms) of the predictor and MI (absence of MI as reference category). Proportionality of the hazard functions will be assessed by visual inspection of hazard plots and Schoenfeld residuals. When proportionality was doubtful, weighted Cox regression models would be fitted.

A two-tailed analysis will be performed and a p value <0.05 will be considered as statistically significant. Statistical analyses will be performed using R software version 4.2.1 (CRAN®, R Core 2021) (and its packages *survival*, *survminer*, *coxphw* and *Hmisc*) (18).

Data privacy and data protection

Privacy issues related to this project have been analyzed with Policlinico Gemelli Data Protection Officer (D.P.O.). As a GENERATOR RWD study, this project will be compliant with GDPR Italian and European directives and regulation (EU Directive 2016/679 and under Italian Laws: Decreto Legislativo 196/2003, Decreto Legislativo 101 2018, Autorizzazione Generale Garante 9/2016)

The guidelines for data privacy are covered by two main documents prepared with the D.P.O.:

- Generator main document “Linee Guida Utilizzo Real World Data” which prescribes the governance mechanisms for Generator through two main bodies (Comitato di Supervisione and Comitato Operativo) where representatives appointed from IRCSS and other key Units of Policlinico participate and have mandate to decide;
- “Orizzonte Normativo Real World Data” prepared by the D.P.O., which provides the directives for the execution of any Generator study to assure its compliance with European and Italian GDPR directives.

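### Secondary endpoint 2 promises a prediction model for 12-month events, but the planned Cox outputs do not show how well it predicts or how much myocardial injury adds

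*Protocol*

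**What the plan says.** **The aim.** Secondary endpoint 2 states that injury during the index hospitalization "will be included in a prediction model and correlated with future cardiovascular events (MACE" and the other 12-month outcomes. Secondary endpoints 1 and 3 speak only of correlation, so the prediction-model wording is particular to endpoint 2. Secondary objective 3 asks whether injury "predicts a worse clinical outcome in terms of major adverse cardiovascular events (MACE" and the other event groups. The third hypothesis, stated just before the Objectives, gives the intended use: "thus helping in the prognostic stratification of COVID-19 patients".

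**The analysis.** For the 12-month outcomes, the Statistical analysis section sets out "to assess whether the presence of myocardial injury during COVID-19 predicts a worse outcome" and says that "uni- and multivariable interaction proportional hazard Cox regression models will be computed". It adds that "multivariable interaction Cox models will be fitted, and the interaction hazard ratios (IHR) evaluated", with one such model for each predictor. The only check on these models is that "Proportionality of the hazard functions will be assessed by visual inspection of hazard plots and Schoenfeld residuals", with weighted Cox regression as the fallback. Significance is two-sided at 0.05.

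**The performance measures.** The same section does name such measures: a Hosmer-Lemeshow test with 10 groups for calibration, and "Model performance will be assessed through receiver-operator characteristic (ROC) curve analysis" (area under the curve, sensitivity, specificity, likelihood ratios). Both come directly after the logistic models for occurrence of injury and before the Cox analysis is introduced.

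**The concern.** The endpoint sets two tasks for the 12-month outcomes: to relate injury to later events, and to put injury in a prediction model. The analysis text covers the first. For the second it names no measure of discrimination, calibration or validation, and no comparison of models with and without injury. Since each predictor gets its own interaction model, it is also unclear which fitted model is the prediction model.

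This matters because the stated use is prognostic stratification. A hazard ratio describes relative hazard between injured and uninjured patients. It does not say how well the whole model ranks patients, whether its predicted 12-month risks are right, or how far injury changes either. If the plan is followed as written, these questions about endpoint 2 stay open, although the data to answer them will have been collected.

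**Working it through.** The protocol gives no event count, hazard ratio, power or C-index for the 12-month analysis, so there is no figure to reproduce. The check has two parts.

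**1. Do the stated measures reach the 12-month model?**

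| Item | Logistic model for occurrence of injury | 12-month Cox models |
|---|---|---|
| Effect measure | Odds ratio with 95% CI | HR and interaction HR |
| Calibration | Hosmer-Lemeshow, 10 groups | none named |
| Discrimination | ROC, AUC, sensitivity, specificity, LR | none named |
| Assumption check | none named | proportional hazards |
| With and without injury | not applicable | none named |

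Nothing extends the first column's measures to the second, and as specified they are for a binary outcome. The prediction-error example under Sample size calculation does not fill the gap: it is a sample-size argument citing work on binary logistic prediction models.

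**2. Could a significant HR go with a small gain in prediction?**

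*Inputs from the protocol:* N about 2000; two-sided alpha 0.05; 12 months of follow-up.

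*Assumptions:* injury prevalence p = 25% (the event fraction in the sample-size example, borrowed here); 12-month event risk 5%, 10% or 15%; true HR 1.5, 1.8 or 2.0; no loss of patients.

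Number of events: D = 2000 × risk = 100, 200 or 300.

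Smallest significant HR (Schoenfeld approximation) = exp(1.96 / √(D·p·(1−p))), with p(1−p) = 0.1875:
- D = 100: exp(1.96/4.330) = 1.57
- D = 200: exp(1.96/6.124) = 1.38
- D = 300: exp(1.96/7.5) = 1.30

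Power = Φ(ln HR · √(D·p·(1−p)) − 1.96). For example, HR 1.8 with D = 100 gives Φ(0.588 × 4.330 − 1.96) = Φ(0.585) = 72%.

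The gain in Harrell's C was simulated with 400,000 patients per scenario. The background was one risk score with log-hazard SD 0.8 or 1.0 (base C 0.707 to 0.770), independent of injury or positively related to it. C for the score alone was compared with C for the score plus injury, using the true coefficients, so there is no overfitting.

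| True HR | Power at 100 / 200 / 300 events | Gain in C |
|---|---|---|
| 1.5 | 42% / 70% / 86% | 0.003-0.006 |
| 1.8 | 72% / 95% / 99% | 0.006-0.011 |
| 2.0 | 85% / 99% / >99% | 0.010-0.017 |

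With prevalence varied from 15% to 35%, the HR detectable with 80% power runs from 2.19 (5% risk, 15% injured) to 1.40 (15% risk, 35% injured). The power formula ignores any correlation of injury with the covariates, which would lower the power of the adjusted test.

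**The case against.** **Detail for a separate SAP.** Only the protocol is shown, and a C-index for a secondary model is detail that a SAP commonly supplies. That has weight against any complaint of mere omission. But the protocol's own Statistical analysis Plan section assigns performance measures to one model and none to the outcome for which its endpoint names a prediction model. That is an internal mismatch.

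**A Cox model containing injury is a prediction model, and its adjusted HR shows that injury predicts.** Much of this stands. In the prognostic-factor sense, the adjusted HR answers the question. The injury coefficient tests whether injury adds prognostic information given the covariates, and a likelihood-ratio test of the models with and without injury has the same null hypothesis. In 450 simulated trials (N = 1800, about 141 to 144 events, HR 1.0, 1.5 or 2.0), the Wald and likelihood-ratio tests agreed at 0.05 every time. What the HR leaves out is the performance of the model and the size of injury's contribution to it.

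**A small gain in C does not mean injury is unimportant.** This stands. At HR 2.0, with 25% injured and 8% overall risk (assumed), the uninjured risk r solves r × (0.75 + 0.25 × 2) = 8%. So r = 6.4%, against 12.8% in the injured, treating the HR as a risk ratio. That contrast may matter clinically although C moves by little more than 0.01. No threshold for a worthwhile gain follows from the documents.

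**Stronger readings.** A reader might infer that a significant HR would be reported as improved risk prediction, or that the study cannot answer endpoint 2 at all. The documents support neither. No passage sets such a reporting rule, the 0.05 level is a general one, the hypothesis is worded as a possible association, and the correlation part of the endpoint is answered.

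**Conclusion.** The point holds as a mismatch between secondary endpoint 2 and the analysis planned for it. The planned outputs will show whether injury is an independent prognostic factor for 12-month events. They will not show how well the 12-month model predicts, or how much injury contributes.

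The mismatch rests on the text alone. Its size rests on assumed prevalence, event risk and background discrimination: an HR of 1.5 to 2.0 may well be significant while C rises by about 0.003 to 0.017. Significance is far from assured at the lower end (42% power for HR 1.5 with 100 events). The figures show that such a result is realistic; they do not forecast it. The matter affects a secondary endpoint of an observational study that describes itself as a pilot, and leaves the primary analysis untouched.

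**What to change.** In the Statistical analysis section, add for 12-month MACE one multivariable Cox model with a fixed set of clinical predictors, fitted with and without injury. Beside the adjusted HR for injury, report the bootstrap-corrected C-index of each model, the change in C with its 95% CI, and 12-month calibration of each.

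If the sponsor does not want a prediction analysis, delete the prediction-model wording from secondary endpoint 2 and present the result as an adjusted association.

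The first option needs a few lines of text and code and no new data; Hmisc, already among the listed packages, computes a C-index. The cost is a little more analysis, and the apparent prognostic value of injury may look smaller.

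### Injury-by-predictor interaction tests are run for every predictor, on MACE and its components, at one unadjusted p<0.05 with no exploratory label, so the chance of a false synergy is well above 5%

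*Protocol*

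**What the plan says.** The last part of the Protocol's Statistical analysis section deals with 12-month outcomes. It plans Cox models "in term of both MACEs at 12 months and single components, uni- and multivariable interaction proportional hazard Cox regression models will be computed". It then adds: "To evaluate combined effects between each clinical/laboratory predictor and presence/absence of Myocardial Injury (MI), multivariable interaction Cox models will be fitted", followed by "In particular, for each predictor, one interaction Cox model will be fitted". Each IHR is to be read as no synergy, reduced hazard or increased hazard according to whether it equals, falls below or exceeds 1.

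The outcomes follow from Secondary objectives, item 3, where MACE is "defined as the composite of cardiovascular death, ischemic heart disease [acute or chronic coronary syndromes], stroke/transient ischemic attack [TIA] and hospitalization for heart failure". That is four components, or five outcomes with MACE itself.

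The decision rule closes the section: "A two-tailed analysis will be performed and a p value <0.05 will be considered as statistically significant". It is the only significance rule in the document. The section neither lists nor counts the predictors and mentions no adjustment. It does not set the interaction tests apart as exploratory.

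**The concern.** The number of interaction tests is the number of predictors times the number of outcomes, and each is judged at 0.05 on its own. The predictor side is open-ended. Variables and procedures lists eight classes of data, including comorbidities, vital signs, symptoms, laboratory results, blood gases and medications. With such a grid, some IHRs will probably cross 0.05 even if injury acts the same way in every patient.

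What is at stake is how the interaction results are read. The plan gives each IHR a substantive meaning, and the study aims to support prognostic stratification after COVID-19. A reader of the results could not tell a chance IHR from a real modifier of the injury effect.

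**Working it through.** The Protocol states no familywise error rate, number of interaction tests or power for interaction, so there is no figure of its own to reproduce.

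**Inputs from the Protocol**
- Threshold: 0.05 two-sided (Statistical analysis).
- Models: one per predictor (Statistical analysis).
- Outcomes: 1 if the interaction models are read as covering MACE only, 5 if they cover MACE and its four components, as the text indicates.

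**Assumed input: number of predictors, P**
- P = 8 is the only predictor count printed. It appears in Sample size calculation as an illustration for a prediction model at N=400, not as the number of interaction models.
- P = 25 is a larger value, chosen to show the range.

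**Formulas, with no true interaction and m = P × outcomes**
- Expected false positives = 0.05 × m. This does not depend on correlation between tests.
- Chance of at least one, independent tests = 1 − 0.95^m.

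| P | Outcomes | m | Expected false positives | At least one (independent) |
|---|---|---|---|---|
| 8 | MACE only | 8 | 0.05 × 8 = 0.4 | 1 − 0.95^8 = 34% |
| 8 | 5 | 40 | 0.05 × 40 = 2.0 | 1 − 0.95^40 = 87% |
| 25 | MACE only | 25 | 0.05 × 25 = 1.25 | 1 − 0.95^25 = 72% |
| 25 | 5 | 125 | 0.05 × 125 = 6.25 | 1 − 0.95^125 = 99.8% |

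**Correlation.** The tests are not independent: the components make up MACE, predictors overlap, and all models use the same patients. Correlated normal test statistics were simulated (100,000 draws; correlation between predictors 0 to 0.5, MACE with component 0.49 or 0.6, component with component 0 or 0.3). At 8 × 5 the chance of at least one false positive was 69-84%, against 87% under independence. The chance of three or more was 29-33%, against 32%. At 20 × 5 the chance of at least one was 89-99%.

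**Sparse events.** The value 0.05 × m is an upper figure if component events are few. Null interactions were simulated with N=2000, 25% injured at doubled risk, a binary predictor with 30% prevalence, Wald tests and a logistic approximation to the Cox model. The share significant was about 4.4% at 5% incidence and 1.3% at 1% incidence; a separate check at about 1% incidence gave 1.8%. Taking MACE at 5% and each component at 1% incidence, 25 predictors give 25 × 0.044 + 100 × 0.013 = 1.1 + 1.3 = 2.4 expected false positives instead of 6.25. Continuous predictors stayed near 5%, so the true figure depends on the mix. The incidences are assumptions, since the Protocol gives no event counts.

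**The case against.** **A separate SAP may list the predictors and the adjustment.** This stands for the missing list, which is not itself the point. It does not dispose of the rule: the Protocol already fixes a model for every predictor and one threshold for all tests. An SAP that controlled error would have to depart from that text.

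**The interactions are supplementary, in a self-described pilot.** No objective or endpoint mentions interaction, which limits the weight of the point. But Sample size calculation uses the pilot status only to waive a formal calculation. It does not label any test exploratory.

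**The IHR is interpreted by its value, and p<0.05 is a general default.** That is fair as a description. Still, the default carries no exception, so it applies to the interaction tests.

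**Stronger readings that the Protocol does not support**
- A reader might infer that several false synergies are almost certain. That needs roughly 20 to 30 predictors tested on five outcomes, with tests near the nominal 5%. At 8 predictors, three or more arise in only about a third of cases.
- A reader might infer that most significant IHRs would be chance findings. The false share is 0.05(1 − π) / [0.05(1 − π) + π × power], where π is the share of real interactions. With π = 5% and power 20% it is 0.0475/0.0575 = 83%. With π = 20% and power 50% it is 0.04/0.14 = 29%. The Protocol gives neither input.
- A reader might tie the interaction tests to the hypothesis about more aggressive therapy and closer follow-up, or take vaccination as the natural first modifier. That hypothesis concerns injury itself, and vaccination is named there as a possible predictor of, or protection against, injury, not as a modifier of its 12-month effect.

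**Conclusion.** The point holds in a limited form. Followed as written, the plan tests an open-ended set of interactions, each at an unadjusted 0.05, and the chance of at least one false synergy exceeds 5% by a wide margin in every scenario shown. The lowest is 34% (8 predictors, MACE only, independent tests). With 8 predictors and five outcomes it is about 69-87%, if each test holds its nominal 5% level.

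The exact size cannot be fixed from the Protocol. It rests on the assumed number of predictors, on whether components are included, on correlation, and on how far sparse component events pull Wald tests below 5%. The primary objective and the main effect of injury on MACE are not affected. This is worth correcting before analysis, but it does not undermine the study.

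**What to change.** In the Protocol's Statistical analysis section, next to the significance rule:

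1. State that the 0.05 threshold does not apply singly to the interaction tests.
2. Name in advance a short list of candidate modifiers for MACE, and apply either Holm or Benjamini-Hochberg control over that list.
3. Report all other IHRs, including all those for the single components, as exploratory estimates with 95% CIs and no claim of significance.

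Component interactions need not be dropped, and no single key 12-month test has to be declared; those are matters of preference. The cost is a few sentences and no extra data. The downside is that fewer interactions can be called significant.
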